- n. Blood and plasma samples will be collected for biobanking if specifically allowed by local EC/IRB; 1 tube of whole blood (prep D1) and 1 tube of plasma (prep B1) will be collected at the time points indicated in the Schedule of Activities. B1 and D1 samples will also be collected at the time of first response, where response is a major cytogenetic response for CP patients and a hematologic response for AP/BP patients when feasible. These additional biobank response samples should be obtained at the next scheduled visit if the next scheduled visit occurs within 2 months after the first response. If the next scheduled visit occurs >2 months after the first response, the sample should be collected at an unscheduled visit within 2 months after the first response, if feasible, unless this is the End of Treatment visit. If not collected on the designated collection day, collect at the next available time point when biospecimens are being collected in conjunction with a subject visit.
- o. End of Treatment visit should be done at Week 208 for those patients completing 4 years on bosutinib therapy, or at any time the patient meets any of the criteria for early discontinuation of bosutinib, whichever is earlier. Patients continuing to receive benefit from bosutinib at the time of study conclusion may switch to commercially available therapy. Note: 1 year = 52 weeks.
- p. Patients discontinuing treatment prior to 4 years from first dose will be followed for survival (telephone contact acceptable) until the patient has completed at least 4 years on study (from time of first dose) or sooner if the patient withdraws consent for disclosure of future information.
- q. Hepatitis B serology testing will be included in the screening tests and throughout the study as clinically indicated. Hepatitis B reactivation has been reported with Tyrosine Kinase Inhibitors (TKI's).

TABLE OF CONTENTS

TABLE OF CONTENTS.....	18
LIST OF TABLES	21
APPENDICES	21
1. INTRODUCTION	22
1.1. Indication.....	22
1.2. Background and Rationale	22
1.2.1. Therapeutic Options for CML	22
1.2.2. Bosutinib (BOSULIF®)	23
1.2.3. Study Rationale.....	28
2. STUDY OBJECTIVES AND ENDPOINTS.....	29
3. STUDY DESIGN.....	30
4. PATIENT SELECTION	31
4.1. Inclusion Criteria.....	31
4.2. Exclusion Criteria.....	33
4.2.1. Philadelphia Chromosome Negative (Ph-) CML Patients.....	34
4.3. Special Warnings and Precautions	34
4.4. Life Style Guidelines.....	35
4.5. Sponsor's Qualified Medical Personnel	36

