6. STUDY PROCEDURES

Refer to the Schedule of Activities ([Table 1](#)) for the complete list of procedures to be performed and associated timepoints. All patients will participate on study for at least 4 years. In view of the very refractory nature of the patients being treated on this study, the investigator may delegate certain specific tests/visits to be performed at other sites closer to the patient's home. The investigator will be responsible for capturing results of any study-specified tests and visits (e.g., AE/Adverse Drug Reaction data collection) that are performed outside his/her site in the relevant CRFs and in the source documents maintained on site. Disease assessments will be performed at the site at week 1, week 2, week 3, week 4 and week 8 during the first 2 months, afterwards (from week 13), the disease assessments will be performed during the 3 monthly visits and starting after week 52, performed during the 6-monthly visit.

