6.2. Study Period

The following procedures will be performed on treatment. Patients must be registered to the study after eligibility is confirmed within 3 days prior to receiving first dose of bosutinib.

Week 1 (Day 1, pre-dose and Day 7), Week 2, Week 3, Week 4 and Week 8 (± 1 day) on Day 7

- Hematology panel ([Appendix 9](#)); complete hematological assessment response;
- Liver function tests ([Appendix 9](#));
- Chemistry panel; including HbA1C, cholesterol, HDL, LDL, potassium, and magnesium, if clinically indicated ([Appendix 9](#));
- Coagulation tests ([Appendix 9](#));

- Urine or serum pregnancy test (for women of childbearing potential) (pre-dose Week1 Day 1 only) ([Appendix 9](#));
- Contraceptive check: patients of child-bearing potential will be required to affirm their use of 2 highly effective methods of contraception which will be documented in the patient's source document;
- Extramedullary disease assessment, if clinically indicated. Sites of extramedullary disease identified at screening should be followed during the course of treatment. Patients should be evaluated upon suspicion of new extramedullary disease;
- Hepatitis B serology testing, as clinically indicated;
- Patient diary card review ([Appendix 6](#));
- Bosutinib dispensation on Day 1.

Week 13, Week 26, Week 39, Week 52 (± 7 days), Week 78, Week 104, Week 130, Week 156, and Week 182 (± 21 days)

- Complete physical examination to include vital signs (sitting or supine blood pressure, heart rate and weight);
- Current smoking status.
- Extramedullary disease assessment, if clinically indicated. Sites of extramedullary disease identified at screening should be followed during the course of treatment. Patients should be evaluated upon suspicion of new extramedullary disease;
- Hepatitis B serology testing, as clinically indicated;
- ECG assessment, if clinically indicated;
- ECHO or MUGA scan assessment, if clinically indicated;
- Chest X-ray, if clinically indicated;
- ECOG Performance Status ([Appendix 8](#));

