6.3. End of Treatment Visit (± 7 days)

The End of Treatment visit should be performed **for all patients** once they have permanently discontinued bosutinib. The visit should occur within the 28 days after the last dose of bosutinib. For patients who discontinue bosutinib prior to Week 208, all procedures listed should be performed, unless collected within the previous 6 weeks. The following procedures are required:

- Complete physical examination including vital signs (sitting or supine blood pressure, heart rate, and weight);
- Current smoking status;
- Extramedullary disease assessment;
- ECOG performance status ([Appendix 7](#));
- FACT-Leu administration ([Appendix 10](#));
- ECG;
- ECHO or MUGA scan; screening and End of Treatment tests to evaluate the cardiac function should use the same test in both visits);
- Chest X-ray;
- Bone marrow aspirate for morphology (% bone marrow differential) and conventional cytogenetic assessment is required if the discontinuation is due to progression and/or failure;
- qRT-PCR for molecular response assessment (BCR-ABL fusion transcript levels) and mutational analysis of the BCR-ABL kinase domain will be performed by a central laboratory. For CP CML, the assessments will be performed using peripheral blood sample. For Advanced Phase CML (AP and BP) the assessment will be performed using peripheral blood and/or bone marrow samples;
- Hematology panel ([Appendix 9](#)); complete hematological assessment response;
- Liver function tests ([Appendix 9](#));

- Chemistry panel; including HbA1C, cholesterol, HDL, LDL, potassium and magnesium, if clinically indicated ([Appendix 9](#));
- Coagulation tests ([Appendix 9](#));
- Urine or serum pregnancy test ([Appendix 9](#));
- Contraceptive check: patients of child-bearing potential will be required to affirm their use of 2 highly effective methods of contraception until 28 days after their final dose of bosutinib which will be documented in the patient's source document;
- Blood and plasma collection for biobanking, if specifically allowed by local EC/IRB, if feasible;
- Final review of patient diary card;
- Return of unused bosutinib. (Note: Ph+ CML patients who receive a prescription [per local regulations] will have a final compliance check for dose levels and duration of Bosutinib treatment).

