7.1.1.4. Molecular Response Assessment

Blood samples (for CP, AP, and BP CML patients) and bone marrow samples (for AP and BP CML patients) will be collected at each efficacy time point for qRT-PCR analysis of BCR-ABL transcript levels that will be reported using the International Scale.

See [Appendix 11](#) for response criteria definitions.

A BCR-ABL1 expression of $\leq 0.1\%$ corresponds to MMR with $>5,000$ ABL1 transcripts.

The following criteria will be used to define deep molecular response (MR):

- MR4 = either (i) detectable disease with $<0.01\%$ BCR-ABL1^{IS} or (ii) undetectable disease in cDNA with $>10\,000$ ABL1 transcripts.
- MR4.5 = either (i) detectable disease with $<0.0032\%$ BCR-ABL1^{IS} or (ii) undetectable disease in cDNA with $>32,000$ ABL1 transcripts in the same volume of cDNA used to test for BCR-ABL1.

Samples with a total of $<10,000$ ABL1 transcripts (i.e., sum of the replicates if replicate analysis is performed) should be considered as not evaluable for MR4 and samples with a total of $<32,000$ ABL1 transcripts should be considered as not evaluable for MR4.5.

MMR is MR3. For all patients, MR1/MR2, MR3 will be used and have a working definition of $\leq 10\%/1\%/0.1\%$ BCR-ABL1^{IS} with $>5\,000$ ABL1 transcripts.

Molecular response assessments will be carried out by an independent central laboratory at baseline and every 3 months until Week 52, then at 6-month intervals during Years 2, 3, and 4 and End of Treatment, and any time there is treatment failure and/or disease progression.

Loss of MMR must be confirmed by 2 consecutive assessments, one of which is $\geq 1\%$ on the International Scale. Note: if confirmation is lacking and the patient goes off treatment due to progressive disease, the assumption is that loss of MMR is confirmed for this study.

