- *For AP, at least one of the following criteria:*
 - *Development of confirmed BP;*
 - *Loss of previous hematologic response over a 2-week period;*
 - *Loss of CHR is defined as:*
 - *WBC count that rises to $>20.0 \times 10^9/L$;*
 - *Platelet count that rises to $\geq 600 \times 10^9/L$;*
 - *Appearance of extramedullary disease not present at baseline including hepatosplenomegaly by palpation or other extramedullary involvement proven by biopsy;*
 - *Appearance of $\geq 5\%$ myelocytes + metamyelocytes in the peripheral blood or appearance of blasts or promyelocytes in the peripheral blood.*
 - *No decrease from baseline levels (if considered clinically relevant) in percentage blasts in peripheral blood or bone marrow on all assessments over a 4-week period.*
- *For BP (of any phenotype):*
 - *Increasing blasts (if considered clinically relevant) peripheral blood or bone marrow over a 4-week period.*

For DOR and PFS, if there is an unacceptable gap between the date of progression or death and the date of the most recent prior disease assessment (>52 weeks), the event will not be used and censorship will be at the most recent prior assessment.

Time to on-treatment transformation, defined by the first progression bullet above, is the time from first dose to confirmed transformation ([date of transformation – first dose date +1]/30.4). Confirmed transformation is defined as 2 consecutive assessments at least 1 week apart or 1 assessment confirmed by progression of disease or death due to any cause. The date of confirmed transformation is the date of the first transformation. Patients without events are censored at the last hematologic or extramedullary assessment where transformation could be assessed.

BCR-ABL mutational status at baseline and treatment discontinuation will be assessed. Emergent mutations are defined as those mutations which were not present at baseline. Patients who were not assessed for baseline mutations are not assessable for emergent mutations.

OS is defined as the time from first dose to the date of death ([date of death – first dose date +1]/30.4). Patients who have not died will be censored at the last known alive date.

For Ph- CML patients, cumulative best response anytime on treatment will be provided. The hierarchy to assess for best response is MR^{4,5}, MR⁴, MMR, MR² (≥ 2 -log reduction), MR¹ (≥ 1 -log reduction), CHR, and OHR.

PRO endpoints are defined in the outcomes research section.

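### The 52-week gap limit for DOR and PFS equals two 26-week visit intervals, so after one missed visit in Years 2–4 visit timing decides whether a progression found at the next scheduled visit counts

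*SAP*

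**What the plan says.** SAP 6.1 (Exploratory, after the progression criteria) sets a rule for DOR and PFS. It measures the time from a progression or death back to "the most recent prior disease assessment (>52 weeks), the event will not be used", and censors the patient at that prior assessment. The SAP gives no reason for 52 weeks. It does not define *disease assessment* for this rule or say how visit windows enter it. The protocol's own definitions of DOR (9.2.2) and PFS (9.3) contain no gap rule.

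The visit calendar is in the protocol. Section 6 places disease assessments, "starting after week 52, performed during the 6-monthly visit". Section 6.2 lists those visits as "Week 78, Week 104, Week 130, Week 156, and Week 182", each with a window of 21 days either way; Week 52 has 7 days either way. Section 7.1.1.4 has molecular assessments every 3 months to Week 52, "then at 6-month intervals during Years 2, 3, and 4 and End of Treatment". Footnote o of Table 1 says the "End of Treatment visit should be done at Week 208 for those patients completing 4 years on bosutinib therapy", and notes that "1 year = 52 weeks". Section 6.3 gives the End of Treatment visit a window of 7 days either way.

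**The concern.** A gap rule is meant to set aside events whose date is too uncertain because the patient went unobserved for too long. Its limit should therefore fall between two recognisable situations, such as one missed visit and two. Here it falls at the centre of the one-missed-visit case. A progression found exactly on schedule (364 days) is kept, and one found a day later is dropped.

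Two features make this more than untidy. First, the rule acts only on events. A patient with the same long gap and no progression keeps event-free time up to the last assessment, so the rule removes failures and never successes. Second, SAP 8.2.2 treats one missed visit the other way for landmark responses: a patient who misses Week 78 but responds at Weeks 52 and 104 counts as a responder at Month 18. If that patient had progressed at Week 104, the event could be deleted on visit timing alone.

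The endpoints exposed are duration of CCyR and of MMR (secondary), and PFS and the other DOR endpoints (exploratory).

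**Working it through.** **Inputs.** Limit: more than 52 weeks, that is more than 364 days (SAP 6.1). Visits: Week 52 ±7 days; Weeks 78, 104, 130, 156 and 182 ±21 days (Protocol 6.2); Week 208 ±7 days (Table 1 footnote o, Protocol 6.3).

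**The plan's figure.** The 52 weeks is a chosen limit with no derivation to reproduce. It equals 2 × 26 weeks, the nominal gap after one missed visit.

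**Range of the gap.** Gap = nominal gap + d2 − d1, where d1 and d2 are the deviations in days of the two attended visits. The range is the nominal gap ± the sum of the two windows.

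- 78→130, 104→156, 130→182: 364 ± (21 + 21) = 322 to 406 days = 46 to 58 weeks.
- 52→104, 156→208: 364 ± (7 + 21) = 336 to 392 days = 48 to 56 weeks.

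**Share above the limit.** Assume d1 and d2 are independent and uniform over whole days in their windows. By symmetry P(gap > 364) = (1 − P(d1 = d2))/2.

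- Both windows ±21 days: 43 × 43 = 1,849 date pairs, 43 of them ties; (1,849 − 43)/2 = 903; 903/1,849 = 0.488.
- One ±7 and one ±21: 15 × 43 = 645 pairs, 15 ties; (645 − 15)/2 = 315; 315/645 = 0.488.

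The result depends little on uniformity. With normal timing around the planned dates (78→130, simulated), the share is 45.4%, 47.9% and 48.7% for a standard deviation of 3, 7 and 10 days per visit. Under uniform timing, 32% to 35% of date pairs lie within 7 days of the limit.

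**Comparison cases** (progression found at the next scheduled visit):

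| Situation | Gap in weeks | Share discarded |
|---|---|---|
| No missed visit, Years 2–4 | at most 32 | 0% |
| One missed visit in Year 1 (longest: 39→78) | at most 43 | 0% |
| One missed visit, Years 2–4 | 46–58 or 48–56 | 48.8% |
| Two missed visits, Years 2–4 | 72–84 or 74–82 | 100% |

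Any limit from 58 to below 72 weeks therefore separates one missed visit from two in Years 2–4.

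**Deaths.** A death date has no visit window. With the death uniform between the close of the missed visit's window and the next visit (an assumption), simulation puts 3.2% to 4.2% beyond 364 days across the five visit pairs.

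**Direction.** Let n patients be at risk just after the prior assessment, with k other events before the progression and no other censoring. If the progression is kept, the Kaplan-Meier factor over the interval, progression included, is (n − k − 1)/n. If it is dropped and the patient is censored at the prior assessment, the factor is (n − k − 1)/(n − 1), which is larger whenever anyone is still event-free. The curve is therefore raised from the event time onward. Before that it can be slightly lower, 1 − k/(n − 1) against 1 − k/n, because the risk set loses a patient early.

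**The case against.** The 49% is conditional on three things: a missed visit, no disease assessment in between, and a progression that surfaces only at the next scheduled visit. The protocol works against that combination. Unplanned visits are allowed, blood counts are taken as clinically indicated, marrow is required at suspected progression, and drug is dispensed only to cover the time to the next resupply visit. A progression found at an unplanned visit before the next scheduled one will normally fall inside 52 weeks. PFS censoring in SAP 6.1 accepts any cytogenetic, hematologic or laboratory assessment at which progression could be assessed. If the gap rule is read the same way, one interim blood count resets the clock for PFS. All of this stands and narrows the point.

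Three stronger readings are tempting and are not supported:

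- A reader might infer that on-treatment deaths are lost at the same rate. They are not: about 3–4% by the check above. OS has no gap rule.
- A reader might infer that all DOR events are exposed. The rule names progression and death, while SAP 6.1 lists confirmed loss as a separate DOR event. The separation is not clean in chronic phase, where loss of CCyR also appears among the progression criteria.
- A reader might contrast this with Year 1 as tolerating three missed visits. It does not do so reliably: missing Weeks 26, 39 and 52 leaves 13→78, nominally 65 weeks.

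It is also fair to say that a kept event is dated at late detection, which lengthens duration too, and that SAP 8.2.2 reports more than 80% of patients off treatment by March 2020, so few may be affected. Neither explains why the limit should sit at the centre of the one-missed-visit range.

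**Conclusion.** The point holds in a limited form. For a progression first detected at the next scheduled visit after one missed visit in Years 2–4, with no interim disease assessment, the 52-week limit keeps or discards the event almost by coin toss: 48.8% discarded under uniform timing within the windows, 45–49% under clustered timing. Every discard favours longer DOR and PFS from the event time onward.

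The number of such events cannot be computed, because the documents give no missed-visit rate; it could be zero. The Week 52 primary response rates and OS are untouched, and SAP 4 plans no hypothesis tests. This is a cheap improvement of minor severity. The undefined term *disease assessment* belongs to the same correction, since it decides how often the rule applies at all.

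**What to change.** In SAP 6.1:

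1. For events after Week 52, set the gap limit at more than 58 weeks. That is two 26-week intervals plus 3 weeks of window at each end. In Years 2–4 one missed visit gives at most 58 weeks and two give at least 72, so in-window timing no longer decides.
2. State which assessments count as a *disease assessment* for each endpoint (duration of CCyR, duration of MMR, the other DOR endpoints, PFS), including whether an interim blood count counts.
3. Add one sensitivity run of DOR and PFS that keeps all progressions and on-treatment deaths regardless of gap. The difference in event counts from the main run shows how many events the rule removes.

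The cost is a few lines of SAP text and one extra run. A few more events may be counted, so durations may be slightly less favourable. The new limit follows from the visit calendar alone, so it can be justified without reference to the data.

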6. ENDPOINTS AND COVARIATES

In general, the baseline value will be defined as the last non-missing value prior to first dose, unless specifically stated otherwise. Assessments performed on Week 1 day 1 will be assumed to be pre-dose per the schedule of activities in the Protocol.

An on-treatment evaluation is defined as any evaluation done during bosutinib therapy or within 28 days of last dose.

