- Time to confirmed transformation on-treatment.

The local cytogenetic assessments will be used for the exploratory endpoint analyses for all patients. The local hematologic assessments will be used for the exploratory endpoint analyses for all patients. *Molecular assessments will be performed at a central laboratory. Endpoint analysis for molecular response will be carried out by independent central analysis.*

Time to response is the time from first dose to first response, unconfirmed for molecular and cytogenetic ([date of first response – first dose date +1]/30.4). Patients without events are censored at the last molecular or cytogenetic assessment where response could be assessed for the respective endpoint.

DOR for MCyR follows the same rules as the secondary endpoint of DOR for CCyR. DOR for MR follows the same rules as the secondary endpoint of DOR for MMR except confirmed loss is defined as 2 consecutive assessments at least 28 days apart with a <4-log (>0.01%) reduction in transcripts from standardized baseline one of which corresponds to a \leq 3-log reduction (\geq 0.1%).

PFS is defined as the time from first dose to objective progression or relapse as assessed by the investigator and noted as the reason for permanent treatment discontinuation on the case report form (CRF) or on-treatment death due to any cause ([date of progression – first dose date +1]/30.4). Patients without events are censored at the last cytogenetic, hematologic, or laboratory assessment where progression could be assessed. Progression is defined as:

- *For CP, at least one of the following criteria:*
 - *Development of AP or BP CML;*
 - *Loss of CHR (in absence of cytogenetic response) confirmed by 2 complete blood counts (CBC) at least 2 weeks apart; Loss of CHR is defined as:*
 - *WBC count that rises to $>20.0 \times 10^9/L$;*
 - *Platelet count that rises to $\geq 600 \times 10^9/L$;*
 - *Appearance of extramedullary disease not present at baseline including hepatosplenomegaly by palpation or other extramedullary involvement proven by biopsy;*
 - *Appearance of $\geq 5\%$ myelocytes + metamyelocytes in the peripheral blood or appearance of blasts or promyelocytes in the peripheral blood;*
 - *Loss of MCyR (loss of CCyR or loss of PCyR);*

- *Increasing white blood count (WBC) in a patient without CHR, defined as doubling of WBC, to $>20 \times 10^9/L$ on 2 occasions at least 2 weeks apart (after the first 4 weeks of treatment).*

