6.2.6. Death

Death data will be collected during this study. Mandatory variables captured are date of death and cause of death. Deaths within 28 days of last dose and death due to study treatment toxicity are safety endpoints.

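### Time to transformation: one AP/BP-range reading counts as confirmed by a later progression or any-cause death, even if later assessments were back outside AP/BP and the death came off treatment

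*SAP*

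**What the plan says.** SAP 6.1, under the exploratory endpoints, measures time to on-treatment transformation from first dose to confirmed transformation. There are two routes to confirmation. The first is repetition: "Confirmed transformation is defined as 2 consecutive assessments at least 1 week apart". The second is "1 assessment confirmed by progression of disease or death due to any cause". Under either route, "The date of confirmed transformation is the date of the first transformation".

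The surrounding rules are tighter:

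- DOR and PFS count only "on-treatment death due to any cause".
- The rule that discards an event more than 52 weeks after the last disease assessment opens "For DOR and PFS, if there is an unacceptable gap between the date of progression or death". Transformation is not named.
- SAP section 6 states: "An on-treatment evaluation is defined as any evaluation done during bosutinib therapy or within 28 days of last dose". This limits when the AP/BP reading can be taken. It does not expressly limit when the confirming death can occur.

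SAP 8.2.3 analyses transformation in the full analysis set by cumulative incidence, with treatment discontinuation without transformation as the competing risk. The protocol does not define confirmed transformation, so it supplies no missing condition.

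**The concern.** The repeat-assessment route keeps a stray reading from counting. The single-assessment route gives up that protection without saying when it may be used. It does not ask whether the next assessments were back in chronic phase, or whether the later event had anything to do with transformation.

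Three consequences follow if the sentence is programmed as written.

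1. An isolated reading that reverts can become an event, dated to the reading.
2. Two patients with identical readings are classified differently at the same early date because of something that happens to one of them later.
3. A patient who stops bosutinib for toxicity and dies during survival follow-up can move from the competing event to an earlier transformation, which shifts both cumulative incidence curves.

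**Working it through.** **Text check.**

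- *Trigger.* SAP Appendix 1 needs only one criterion for the worse phase. The platelet criterion must be persistent and unrelated to therapy. The blast and basophil criteria carry no persistence condition.
- *Confirming progression.* For CP patients SAP 6.1 counts loss of a major cytogenetic response, loss of CHR and a rising white count as progression. None of these is transformation.
- *Confirming death.* Any cause, with no on-treatment limit. Protocol 6.4 follows survival for at least 4 years from first dose, including after discontinuation.
- *Reversion.* Nothing says that a later assessment outside AP/BP cancels the first.

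**Worked patient.** A CP patient has 20% basophils at Week 13, is outside AP/BP at every later visit, and stops at Week 104 for loss of cytogenetic response. The literal rule gives a transformation at Week 13 and a PFS event at Week 104. Yet development of AP or BP is itself a progression criterion, so the two endpoints disagree about the same patient.

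**Longest scheduled span (illustration).** From a Week 13 reading to an event at Week 208 is 208 − 13 = 195 weeks, with 8 scheduled visits between (Weeks 26, 39, 52, 78, 104, 130, 156, 182).

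**Size.** The documents give no rate for this endpoint, so there is no figure to reproduce. Expected spurious share = [1 − (1 − q)^k] × s, where:

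- q = chance that one assessment is an isolated AP/BP-range reading that reverts (assumed 0.5%; range 0.25% to 1%);
- s = share of patients with a later event that could confirm it (assumed 20%; range 10% to 30%). For scale, protocol 1.2.2 gives 80.6% two-year PFS in Study 200 second-line CP, so 1 − 0.806 = 19.4%;
- k = scheduled post-dose hematology assessments before the event. Protocol Table 1 has 15 in all, including End of Treatment. A patient with an event at Week 52 has had 8 (Weeks 1, 2, 3, 4, 8, 13, 26, 39); at Week 104, 10 (adding Weeks 52 and 78);
- N = 106 + 45 = 151, from the enrolment figures in SAP section 2. This slightly overstates the number at risk, because BP patients have no later phase to enter.

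| q | s | k | Share | Patients of 151 |
|---|---|---|---|---|
| 0.25% | 10% | 8 | 0.0198 × 0.10 = 0.2% | 0.3 |
| 0.5% | 20% | 8 | 0.0393 × 0.20 = 0.8% | 1.2 |
| 0.5% | 20% | 10 | 0.0489 × 0.20 = 1.0% | 1.5 |
| 1% | 30% | 10 | 0.0956 × 0.30 = 2.9% | 4.3 |

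**Cross-check by patient.** Suppose 2% to 10% of patients (assumed) have one reverting reading. With the 19.4% two-year PFS event rate, the expected count is 151 × 0.02 × 0.194 = 0.6 to 151 × 0.10 × 0.194 = 2.9. With the two-year death rate in the same group (1 − 0.906 = 9.4%) it is 0.3 to 1.4.

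Results are shown by cohort. One spurious case among 45 patients is 1/45 = 2.2 percentage points.

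**The case against.** The strongest reply is that the second route is plainly a substitute for a missing second assessment. Protocol 7.1.1.1, 7.1.1.2 and 7.1.1.4 use such a convention for loss of response: where confirmation is lacking and the patient goes off treatment for progressive disease, the loss is taken as confirmed. That is the likely intent here too. But the protocol writes the condition out each time, and the SAP leaves it out for transformation.

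The progression route is also largely bounded in practice. Development of AP or BP is a reason to stop bosutinib under protocol 5.3, and the PFS definition ties progression to the recorded reason for discontinuation. The worked patient therefore needs an investigator who saw an AP-range value and did not treat it as transformation. This stands as a reason to expect few cases. It does not close the death route.

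Platelet dips caused by treatment, an obvious source of false triggers, are already excluded. Efficacy listings would let a reader inspect each case.

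The 52-week rule would not be a full remedy if extended. It measures the gap from the most recent assessment to the event, so it would remove some late deaths but not a reverted reading in a patient still being assessed.

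**Conclusion.** The wording gap is real: the text neither cancels a reading that reverts nor limits the confirming death to on-treatment. Its effect is probably about one patient in about 150. That rests on assumed reading and event rates, on independence between them, and on 8 to 10 assessments before the event. The endpoint is exploratory and descriptive, with no hypothesis attached, so no primary or secondary result changes.

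A reader might infer three stronger things that the documents do not support.

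- That the SAP expressly allows confirmation at any later time. It does not say so; it is silent on the interval.
- That all 15 scheduled assessments are exposed, which would give (1 − 0.995^15) × 0.20 = 1.5%. Patients who progress or die on treatment stop early, and the reading must come before the event.
- That spurious events could rival true ones, judged against the 2% progression to AP or BP in protocol 1.2.2. That figure is from newly diagnosed CP patients. This trial enrols resistant or intolerant patients across phases and lines, and the documents give no transformation rate for them.

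**What to change.** Amend the sentence in SAP 6.1 so that a single AP/BP assessment is confirmed by progression or death only if:

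1. no later evaluable assessment of the relevant type (hematologic, marrow, cytogenetic or extramedullary) before that event is outside AP/BP; and
2. the progression or death is on-treatment, that is, no later than 28 days after last dose, in line with DOR and PFS.

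Naming the assessment type matters because a major-route clonal abnormality in Ph+ cells is an AP criterion found by cytogenetics. A rule limited to hematologic or extramedullary assessments would miss it.

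The change should not go as far as requiring death from CML. Cause of death is available ("Mandatory variables captured are date of death and cause of death"), but a true transformation may end in a death recorded as infection or bleeding, and counting any cause avoids that attribution.

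The cost is one SAP sentence and the matching program logic, using data already collected. The small downside is that a few true transformations followed by death after the 28-day window become unconfirmed.
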